Cover Page

Official Title of the Study: Validation of Point Partial User Needs With Partial Finger Amputees

Document Date: March 15, 2019

NCT Number: NCT05012657

IRB Conditions
Satisfied at the Protocol
Level
Mar 15, 2019

Western IRB Protocol

Protocol #:

Project Title: The Point Digit: A Family of Ratcheting Prosthetic Finger Technology

Principal Investigator: [name]

Version Date: 8/2/2018

- I. Hypotheses and Specific Aims: The purpose of this research is to study the use of passive prosthetic devices. The design of passive prosthetic devices for amputees will be tested by human subjects for strength, function, and durability. The hypothesis of the study asks whether certain design features can withstand activities of daily living. Examples of activities include lifting objects, pouring water, turning keys, etc.
- II. Background and Significance: There are approximately 500,000 people living with minor upper limb loss in the USA [1],[2]. Minor upper limb loss (also partial hand amputation) is defined as the amputation of the bones distal to the wrist joint. While the field refers to these types of amputation as 'minor,' it can be a severe disability, especially if the amputation involves the thumb and/or multiple digits. In fact, partial hand amputees self-report a higher level of disability compared to other major unilateral upper limb amputees [3]. Furthermore, it was reported that fewer than half of partial hand amputees were able to return to the same job after amputation and most found that the prosthetic devices were insufficient to meet the demands of their work [4]. Amputation can cause physical, psychosocial, and economic damage to an individual and can lead to depression, anxiety, loss of self-esteem, and social isolation [5],[6]. While the number of individuals with partial hand amputation is 10 times more than all other categories of upper limb amputation combined, the state of available technology for this underserved patient population is relatively poor [7].

Outcome measures include completion rate, completion time, SHAP score, DASH score, box and blocks test, clothespin test, and other measures of function. These metrics quantify the performance of prosthetic devices.

B. Description of Population to be Enrolled:

The subject population will consist of a convenient sample of people. The subjects will have various ethnicity, age, and gender. An estimated total of 30 subjects will be enrolled. The subjects must be normal intact individuals and/or persons with amputation who are able to understand and follow directions in English, assessed by their ability to respond during the recruitment and consent process. Exclusion criteria include any subjects that are not able to understand the procedures and/or are less than 18 years of age.

C. Study Design and Research Methods

The experiments will take place at the Point Designs LLC headquarters, at partner clinics, and/or at home. The participant will come up to 3 times for up to 4 hour sessions. During this session the participant will be asked to perform activities of daily living in a laboratory setting. The only devices/materials coming into contact with the participant will be standard of care orthopedic/prosthetic equipment including gauze, casting tape, medical tape, prosthetic sockets. Risks from the above devices are possible minor skin discomfort. Standard of care procedures will be used to mount the prosthetic device. A training period will be followed by several tests to measure the function of the prosthetic device. Different versions of the device may be presented to the subject in a randomized order.

D. Description, Risks and Justification of Procedures and Data Collection Tools:

Risks from the above devices are possible minor skin discomfort. If you feel that you have been harmed while participating in this study, you should inform [name] at [contact] immediately.

E. Potential Scientific Problems:

Potential scientific problems include a lack of subjects with amputation and/or a lack of ability to perform the activities of daily living with the prosthetic devices.

F. Data Analysis Plan:

Data will be processed with standard statistical methods using MATLAB (Mathworks, Inc.) in order to produce the metrics described previously (completion rate, completion time, etc.)

G. Summarize Knowledge to be Gained:

The development of more functional/robust prosthetic devices will augment the quality of life for people with amputation.

H. References:

N/A

Cover Page

Official Title of the Study: Validation of Point Partial User Needs With Partial Finger

Amputees

Document Date: October 22, 2019

NCT Number: NCT05012657

Statistical Analysis Plan

This is not a statistically powered study. This is a device feasibility test with pass/fail results for objective tasks. The validation methods described in Table 1 will be implemented to confirm the user needs of the *Point Partial*. A simple pass/fail result will be recorded for each user need for each subject. No formal outcome measures nor data analysis will be performed during this sub-aim (a statistically powered study is presented in Aim #2.2). Here, we are focused on confirming that the product suits our user needs in its first use by human subjects. An overall passing rate above 80% across all user needs and subjects will be considered a success.

Table 2. User Needs and Validation Methods for Point Partial

User Need		Validation Method	
ID#	Description	ID#	Description
UN-1	Point Partial shall be comfortable for a full day's use	VAL-1	User wears Point Partial(s) for a full day
UN-2	Point Partial shall allow the user to flex and extend finger without their contralateral hand	VAL-2	User flexes and extends the Point Partial(s) without using contralateral hand
UN-3	Point Partial shall be robust enough to operate in challenging environments	VAL-3.1	User lifts a 25 lb. bag with Point Partial(s)
		VAL-3.2	User grips a hammer with Point Partial(s) and drives a nail into a piece of wood
UN-4	Point Partial shall be releasable while performing active grasps	VAL-4	User releases Point Partial(s) while performing an active grasp by pressing the dorsal button
UN-5	Point Partial shall have a durable ratcheting mechanism	VAL-5	User positions Point Partial(s) into each of the locking positions
UN-6	Point Partial shall have a reliable auto spring-back mechanism	VAL-6	User activates spring-back mechanism by using (1) contralateral hand, (2) tabletop, and (3) side or thigh
UN-7	Point Partial shall have high friction	VAL-7	User grips a 5 lb. cylindrical smooth object using Point Partial(s) for 10 seconds
UN-8	Point Partial shall have a pronounced fingernail	VAL-8	User picks up 1 coin from a smooth tabletop
UN-9	Point Partial shall be robustly attached to mounting system	VAL-9	User performs VAL-1 through VAL-8

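### The only success rule pools all needs and subjects into one rate above 80%, so the test can be called a success although one of the nine user needs was not met

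*SAP*

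**What the plan says.** The SAP describes an unpowered study: "This is a device feasibility test with pass/fail results for objective tasks". It gives the purpose as follows: "Here, we are focused on confirming that the product suits our user needs in its first use by human subjects". The table of user needs then sets out nine requirements, UN-1 to UN-9, each worded as something the device shall do and each with at least one validation method.

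The unit of recording is the need within the subject: "A simple pass/fail result will be recorded for each user need for each subject". The unit of conclusion is different: "An overall passing rate above 80% across all user needs and subjects will be considered a success". Neither document gives a minimum for any single need, a list of critical needs or a per-subject criterion. Protocol section IV.F refers only to standard statistical methods.

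One row of the table affects the arithmetic. UN-9 reads "Point Partial shall be robustly attached to mounting system", but its validation method is "User performs VAL-1 through VAL-8". The SAP does not say whether a subject who fails one of those tasks also fails UN-9.

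The SAP gives no number of subjects for this test. The only figure is in Protocol section IV.B: "An estimated total of 30 subjects will be enrolled". It covers the whole protocol and allows intact individuals as well as people with amputation.

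**The concern.** The aim and the data are per need, but the conclusion is an average over needs. The needs are not interchangeable. Picking up a coin (UN-8) says nothing about whether the device can be released during an active grasp (UN-4) or withstands lifting and hammering (UN-3). Under a pooled rate, good results on one make up for bad results on another.

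At stake is the meaning of the word success. A reader told that the test succeeded would take it that the device suits its user needs, because that is the stated aim. A pooled rate above 80% does not show this, yet it is the only stated basis for the conclusion.

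**Working it through.** **Inputs.** From the SAP: nine needs, one result per need per subject, success if the pooled rate is strictly above 80%. Assumed: n = 5, 10 and 30, the last being the protocol's overall estimate. The 80% is a chosen threshold, so there is no plan figure to reproduce.

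**Step 1. Passes needed.** With n subjects there are 9n results. The smallest count above 80% is:
- n = 5: 37 of 45
- n = 10: 73 of 90
- n = 30: 217 of 270

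**Step 2. UN-9 scored on attachment, all else passes.** If one need fails in every subject, the pooled rate is (9n − n)/9n = 8/9 = 88.9%, a success at any n (240 of 270 at n = 30). The same holds if UN-9 is itself the only failed need.

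**Step 3. UN-9 fails whenever any of VAL-1 to VAL-8 fails, all else passes.** Each failure on one of UN-1 to UN-8 now costs two results. If a share f of subjects fails that need, the pooled rate is 1 − 2f/9.
- f = 1 gives 7/9 = 77.8%, not a success.
- 1 − 2f/9 > 0.80 requires f < 0.90.
- n = 5: 4 failures give 37/45 = 82.2%, a success.
- n = 10: 8 failures give 74/90 = 82.2%, a success; 9 give 72/90 = 80.0%, not above.
- n = 30: 26 failures give 218/270 = 80.7%, a success; 27 give 216/270 = 80.0%, not above.

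**Step 4. Illustration when the other needs are imperfect.** These are exact probabilities that the pooled rule declares success. The pass rates are assumed, and tasks and subjects are taken as independent. In the first two rows UN-9 is one of the other eight needs; in the last three it passes only if all eight tasks pass.

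| UN-9 scoring | Pass rate, weak need | Pass rate, others | n = 5 | n = 10 | n = 30 |
|---|---|---|---|---|---|
| Attachment | 0% | 95% | 0.86 | 0.95 | 0.999 |
| Attachment | 0% | 90% | 0.42 | 0.45 | 0.47 |
| Task completion | 50% | 95% | 0.64 | 0.74 | 0.90 |
| Task completion | 50% | 90% | 0.32 | 0.30 | 0.22 |
| Task completion | 20% | 95% | 0.23 | 0.19 | 0.10 |

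The first two rows are P(Bin(8n, q) ≥ 37, 73, 217), where q is the pass rate of the others. The last three convolve the per-subject score over n subjects.

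**Step 5. Would the same 80% applied to each need be a good remedy?** Above 80% on one need means 5/5, 9/10 or 25/30. A need that truly passes at 90% misses this with probability m = 0.4095, 0.2639 or 0.0732. If all nine truly pass at 90% and are independent, the chance that at least one misses is 1 − (1 − m)^9 = 0.99, 0.94 and 0.50 (0.495 before rounding). At n = 5 or 10 such a label would usually fall on at least one good need.

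**The case against.** The strongest reply is that this is a declared feasibility test with no formal data analysis planned and a powered study placed elsewhere. A single overall benchmark is a legitimate choice in that setting. Neither document ties success to an efficacy claim or a go/no-go decision. Results are recorded for each need, so a failed need would be visible. The SAP does not define when a single need counts as met, and it sets 80% only for the pooled rate.

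Most of this stands, and it limits the weight of the point. It does not remove it. The SAP chose to state a success threshold, and that threshold does not answer the question the SAP asks. Nothing commits the sponsor to report or conclude by need.

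A reader might infer that a need met by nobody always goes through as a success. The documents do not support that. If UN-9 is scored on completion of the other tasks, as VAL-9 can be read literally, total failure of one of UN-1 to UN-8 gives 77.8% and the rule catches it. A reader might also infer that a wrong conclusion is likely. That rests on assumed n, pass rates and independence, and tasks done by one user with one device are unlikely to be independent. When the other needs pass at 90%, or UN-9 is scored on task completion, the probability can be well below one half.

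**Conclusion.** The concern holds in a limited form. As written, the rule can declare success although one of the nine needs was not met, under either reading of UN-9. Only the size of the gap changes: failure in every subject (88.9%) if UN-9 is scored on attachment or is itself the failed need, and failure in just under 90% of subjects if UN-9 falls with any task. These counts follow from the SAP's own rule and assume only that all other results are passes. The probabilities in Step 4 are illustrative.

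The point concerns how the conclusion is defined. It does not call for power or a larger sample, and no data would be lost. It should be fixed because the rule, followed exactly, can give a conclusion that the data contradict, and the remedy is cheap.

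**What to change.** 1. Report passes out of n for each of the nine needs and draw the conclusion need by need from those counts. Keep the pooled rate above 80% as an overall summary that does not by itself support the conclusion that the product suits its user needs.
2. Do not attach a fixed 80% cut-off to each need by default, for the reason in Step 5. Any floor for a single need is the sponsor's choice, to be set in advance together with n.
3. State how UN-9 is scored. Scoring it on whether the attachment held during VAL-1 to VAL-8 matches the stated need and avoids counting one task failure twice. It also makes the pooled rate more lenient: 88.9% instead of 77.8% when one other need fails in everyone. Adopt it only together with item 1.

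The cost is a nine-row table from results already recorded, one item on the record form, and a conclusion that may be less favourable than a single statement of success.
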